#### **Document Revision History:**

Version	Date	Content/Modifications
01	08/26/2022	Final Original

Client/Project	Arrivo/Sirtsei 201	
Version and Date	V01 August 26, 2022	

#### 1 Abbreviations

AE Adverse Event

ANCOVA Analysis of Covariance

ATC Anatomical Therapeutic Chemical
BOCF Baseline Observation Carried Foward

CI Confidence Interval

CMH Cochran-Mantel-Haenzel

ECG Electrocardiogram

HAM-D Hamilton Depression Rating Scale

ITT Intent to Treat

LOCF Last Observation Carried Forward

LTFU Lost to Follow-up MAR Missing at Random

MADRS Montgomery-Asberg Depression Rating Scale

MDD Major Depressive Disorder

MedDRA Medical Dictionary for Regulatory Activities

mITT Modified Intent to Treat

MMRM Mixed Model for Repeated Measures

NAD+ Nicotinamide-adenine dinucleotide coenzyme

PP Per-Protocol Population

PT Preferred Term

Q-LES-Q-SF Quality of Life Enjoyment and Satisfaction

Questionnaire

QIDS-SR Quick Inventory of Depressive Symptomology

SAE(s) Serious Adverse Event(s)

SAS® Statistical Analysis Software®

SDS Sheehan Disability Scale
SOC System Organ Class
SD Standard Deviation

SOC System Organ Class SOE Study Order of Events

Form STAT401.V3 Page 4 of 23

Client/Project	Arrivo/Sirtsei 201
Version and Date	V01 August 26, 2022

#### 2 Introduction

#### 2.1 Background

SP-624 is a novel selective activator of intended for the treatment of major depressive disorder, also known as unipolar or major depression. Major depressive disorder is characterized by a persistent feeling of sadness or a lack of interest in outside stimuli, with an estimated 16 million people living with major depression in the United States as of 2012. Antidepressant therapy aims to show symptom remission, often defined as at least 50% improvement from Baseline score on a depression scale such as the Hamilton Depression Rating Scale. However, there is room for improvement with many remitted patients reporting poorer quality of life and running a higher risk of depression relapse.

Phase 1 clinical studies have shown that oral doses of SP-624 up to 30 mg/day were generally safe and well tolerated, without any reports of severe AEs, SAEs, deaths, or AEs leading to withdrawal from the study.

Sirtsei Pharmaceuticals, Inc. plans to investigate the safety and efficacy of SP-624 in this Phase 2, double-blind, placebo controlled, multicenter study in adults with moderate to severe MDD. The study will evaluate the safety and efficacy of a 4-week, multidose regimen of SP-624 versus placebo in approximately 300 subjects. Pending the efficacy and safety profile observed from this study, additional nonclinical and clinical studies will be conducted.

#### 2.2 Changes to Planned Analyses

The protocol definition of the safety population is all subjects in the mITT population who receive at least one dose of study drug. This population definition has been corrected in section 7 below to all subjects that were randomized to treatment and received at least one dose of study drug. The updated safety population definition will be used for all safety analyses.

# 3 Study Objectives

The primary objective of this study is to evaluate the efficacy of SP-624 administered once-daily for up to 4 weeks compared to placebo in the treatment of adults with MDD. Additionally, there are two secondary objectives to evaluate the safety and tolerability of SP-624 administered once-daily for up to 4 weeks compared to placebo in the treatment of adults with MDD and to characterize the population PK of SP-624 in plasma when administered orally to subjects with MDD.

# 4 Investigational Plan and Study Design

This is a Phase 2, multicenter, double-blind, randomized, placebo-controlled study of the safety and efficacy of SP-624 in the treatment of adult subjects with MDD as defined by the DSM-5. Following the successful completion of a Screening Phase, subjects will be randomized to one of two treatment groups in a 1:1 ratio and will receive SP-624 or placebo over a treatment period of four weeks (Treatment Group 1: SP-624 20 mg/day; Treatment Group 2: Placebo).

Approximately 300 subjects in a 1:1 ratio (150 per treatment group) will be enrolled into the study. Each subject will complete Screening, Baseline, Treatment, and Follow-up Visits.

# 5 Sample Size Justification

Recent studies of MDD using change from Baseline in MADRS total scores suggest that placebo will yield an approximately nine unit decrease over four weeks with a standard deviation (SD) of around 9.2. SP-624 is expected to yield at least a 12 unit decrease in MADRS total score over four weeks with a

Form STAT401.V3 Page 5 of 23

Client/Project	Arrivo/Sirtsei 201
Version and Date	V01 August 26, 2022

similar SD of around 9.2. A minimum of 150 subjects per treatment arm (300 total) would be needed to detect a treatment difference of three units with 80% statistical power. The sample size was estimated using NQuery 8 (V8.5.2.0) two group test of equal means (MTT0-1: www.statsols.com).

#### 6 Visit Schedule and Visit Windows

A Screening period of up to 28 days (Day -28 to Day -2) and a Baseline Visit (Day -1) will precede initiation of the Treatment Period. During the Screening Period, all Screening assessments will be completed, and any current depression medications will be discontinued. All Screening assessments should be completed before discontinuing any current depression medications. Subjects who continue to satisfy all entry criteria at the Baseline Visit will be randomized in a 1:1 ratio to one of the two treatment groups. At the completion of the Baseline Visit, randomized subjects will be dispensed study drug and will be instructed to begin dosing the next morning (Day 1).

During the Treatment Period, subjects will be scheduled to return to the clinic for safety and efficacy assessments at the end of Weeks 1, 2, 3, and 4 as specified in the SOE (Table 2 of the protocol). After the final dose of study drug, subjects will complete a Follow-up Period of two weeks and will return at the end of Week 5 (1 week after final dose) and Week 6 (2 weeks after final dose). Subjects may be treated with anti-depressant medications according to physician recommendations after completion of the Week 5 Visit unless a clinically significant lab value is identified at the Week 4 Visit. If a clinically significant lab value is identified at the Week 4 Visit. If a clinically significant lab value needs to be followed prior to initiating new therapy. Unless there are any outstanding safety issues that require follow-up, subjects will be discharged from the study at the Week 6 Visit.

Form STAT401.V3 Page 6 of 23

Client/Project	Arrivo/Sirtsei 201
Version and Date	V01 August 26, 2022

Table 6.1, Sirtsei 201 Study Visit Schedule

Study Period	Screening/ Washout	Baseline		Treatment Period	nt Period		Follow-up Period	p Period
Study Visit	-	2	3	4	w	9	7	8
			Week 1	Week 2	Week 3	Week 4 / Premature D/C	Week 5/ 1-Week Follow-up (7±3 days	Week 6/ 2-Week Follow-up (14 ± 3
Study Day / Week	Day -28 to -2	Day -1	(Day 7±3 Days)	(Day 14±3 Days)	(Day 21±3 Days)	(Day 28±3 Days)	post last dose)	days post last dose)
Event / Assessment								
Clinic Visit 	X	X	X	X	X	X	X	X
Informed Consent	X							
Inclusion/Exclusion	X	X						
Diagnosis Confirmation	X							
and Treatment History								
Height and Weight 	X	X				X		
Physical Exam 	X	X	X	X	X	X	X	
C-SSRS 	X	X	X	X	X	X	X	X
Pregnancy Test 	X	X				X		
Urine Drug Screen	X							
Clinical Safety Labs 	X	X		X		X	X	
Vital Signs 	X	X	X	X	X	X	X	X
12-Lead ECG 	X	X	X	X	X	X	X	
MADRS	X	X	X	X	X	X	X	
CGI-S	X	X	X	X	X	X	X	
HAM-D, SDS, QIDS-RS, Q-LES-Q-SF		X		X		X		
Randomization		X						
Dispensation / Collection / Accountability of Study Drug		X	X	X	X	X		
Plasma PK Blood Sampling		X	X	X		X		

Client/Project	Arrivo/Sirtsei 201
Version and Date	V01 August 26, 2022

	Screening/							
Study Period	Washout	Baseline		Treatme	Treatment Period		Follow-up Period	p Period
Study Visit	1	2	3	4	S	9	7	&
							Week 5/	Week 6/
						Week 4 /	1-Week	2-Week
						Premature	Follow-up	Follow-up
			Week 1	Week 2	Week 3	D/C	(7 ±3 days	$(14 \pm 3)$
	Day -28 to		(Day 7±3	(Day 14±3	(Day 21±3	(Day 28±3	post last	days post
Study Day / Week	-2	Day -1	Days)	Days)	Days)	Days)	dose)	last dose)
Similarina pasia								
Prior and Con Med	X	X	X	X	X	X	X	X
Record								
AE Monitoring	X	X	X	X	X	X	X	X

SR=Quick Inventory of Depressive Symptomology - Self Report; Q-LES-Q-SF=Quality of Life Enjoyment and Satisfaction Questionnaire - Short Form; SDS=Sheehan Disability ECG=electrocardiogram; MADRS=Montgomery-Asberg Depression Rating Scale; PK=pharmacokinetics; Premature D/C=Premature Discontinuation from treatment; QIDS-Abbreviations: AE=adverse event; con med=concomitant medication; CGI-S=clinical global impression-severity; C-SSRS=Columbia-Suicide Severity Rating Scale;

adverse events and concomitant medications. The Screening, Baseline, and Week 4/Premature Discontinuation Visits cannot be done remotely. The sponsor If a clinic visit is not possible (e.g., due to illness), a remote visit may be conducted to complete all assessments that can be done remotely and assess for should be contacted prior to conducting any remote visits whenever possible.

 Height and body weight at Visit 1. Body weight only at Visit 2 and Visit 6/Premature Discontinuation.

 Physical examinations will include a review of the following body systems: general appearance, skin and extremities, ear/eyes/nose/throat, head/neck, heart/chest, abdomen, musculoskeletal, and neurological.

 Baseline/Screening Version at Visit 1; Since Last Visit Version at Visits 2-8.

 All females; Serum pregnancy test at Visit 1 and Visit 6 (or Premature Discontinuation); Urine pregnancy test at Visit 2 – if urine pregnancy test at Visit 2 is positive, a confirmatory serum pregnancy test will be conducted.

 Clinical safety labs include clinical chemistry, hematology, coagulation, and urinalysis. Labs should be collected in a fasting state. Urinalysis not required at Visit 4 (Week 2 visit). Vital signs include blood pressure, pulse rate, and oral body temperature. Vital signs to be assessed in a sitting position after three mins or more of quiet sitting.  Two ECGs to be collected at the Baseline Visit separated by approximately 10 minutes. One ECG collected at all other visits.

Page 8 of 23

Client/Project	Arrivo/Sirtsei 201
Version and Date	V01 August 26, 2022

#### 7 Study Populations

The following populations will be considered for this study:

- All Subjects Population all subjects who sign informed consent and are assigned a unique subject identification number. This population will be used to summarize disposition.
- Modified Intent-to-Treat (mITT) Population all subjects who are randomized to receive
  treatment, receive at least one dose of study drug, and have a Baseline and at least one post-dose
  efficacy assessment. This population will be the primary population used to summarize
  demographics, baseline characteristics, medical history, treatment history, and all efficacy
  outcomes. Subjects will be analyzed according to randomized treatment group.
- Safety Population all subjects randomized to treatment and who receive at least one dose of study drug. Safety subjects will be summarized according to the actual treatment they received. This population will be used to summarize all safety assessments.
- PK Population— all subjects who receive active study drug and have evaluable PK data based on actual treatment received, protocol compliance, adequate numbers of samples, and successful sample assays.

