#### 8 Statistical Methods

#### 8.1 General Reporting Conventions

Study data will be provided in listings and sorted by subject number, study period, and assessment time. The study results will be displayed using descriptive summary tables and inferential analyses completed as described below. Summaries will be displayed by group for all tables and, optionally, for all subjects for baseline tables. For measurements that have multiple intermediate visits, results for observed data will be summarized for each time.

Standard numeric descriptive statistics include number of subjects or records observed (N), mean, standard deviation (std), median, minimum (min), and maximum (max) values. Standard categorical descriptive statistics include the count and percentages of subjects with a level of the variable summarized. Hypothesis tests will assess the null hypothesis that there is no difference in the treatment arms. Two-sided p-values of less than or equal to 0.05 will be considered statistically significant.

All summaries, statistical analyses, and individual subject data listings described below will be completed using Version 9.4 or later of the SAS Statistical Analysis System (SAS Institute, Inc. Cary, NC).

Subjects who are randomized but not treated and those who are treated but have no post-treatment follow-up assessments or data will be listed, but not analyzed. For all listings with dates, the relative study day will be presented, and a minus sign will denote study day is prior to first dose (day 1) while a plus sign will denote number of study days after last dose. Days occurring during treatment period will use neither a plus nor a minus sign.

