#### 8.3.5.1 Primary Efficacy Endpoint

The primary efficacy endpoint for this study is the change from Baseline to Week 4 in total MADRS score. Efficacy analyses will be conducted using the mITT population, assuming subjects had dosed as directed for 4 weeks.

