**Table 8.1, Handling of Intercurrent Events** 

Estimand	Intercurrent Event	Rule / Rationale
Primary	Premature discontinuation /	Hypothetical "as own treatment" strategy. Clinical
	Permanent treatment	course is the same as other subjects in the same
	discontinuation	treatment group, who had not discontinued study
		treatment.
		Exclude observations that occur more than 3 days
		after the last dose of study drug for subjects who
		discontinue. The objective of the study is to
		evaluate the effect of SP-624 subjects who are
		provided drug to take on a standard schedule up to 4
		weeks. After 3 days, the drug should be cleared
		from all subjects, so the inclusion of any such data
		point is inconsistent with the goal of the estimand.
	Drug non-compliance / Missed	Treatment policy strategy.
	study medication	Some degree of non-compliance missed doses
		would be expected to occur in standard use.
	Protocol deviations not leading	Treatment policy strategy
	to study discontinuation	Overall, if not sufficient to lead to subject removal,
		the expectation is that they would not significantly
		impact subject results.
	Concomitant medications in	Treatment policy strategy
	violation of the protocol	This is expected to be a rare event in this clinical
		trial and treatment effect will be estimated
		irrespective of concomitant medication violations.

The hypothetical "as own treatment" strategy was selected for premature discontinuation or treatment discontinuation intercurrent events to evaluate the effect of treatment with respect to its pharmacologic efficacy. For the change from week 4 to week 5 follow-up secondary analysis, only subjects that were included in the week 4 primary analysis will be used. This should provide the most unbiased data for this

Form STAT401.V3 Page 12 of 23

Client/Project	Arrivo/Sirtsei 201
Version and Date	V01 August 26, 2022

phase 2 study to inform future studies. The treatment policy strategy will be used for all other defined intercurrent events.

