#### 8.3.5.5 Sensitivity and Supporting Analyses

A dropout rate of 20-30% is typically seen in MDD studies. Subjects will be grouped by the visit at which they had their last MADRS total score measured. This will result in five categories of discontinuation: Week 1 dropouts, Week 2 dropouts, Week 3 dropouts, Week 4 dropouts, and completers. Mean change from Baseline in MADRS total score will be plotted by the dropout category and by reason for discontinuation, to assess whether this efficacy measure appears to be correlated with study dropout.

The mechanisms that cause missing data may be missing at random (MAR) or may be missing not at random (MNAR). The MMRM model (as implemented within the PROC MIXED procedure in SAS) used in the primary analysis of the primary efficacy endpoint relies on the assumption of MAR.

Therefore, a sensitivity analysis using the tipping-point approach may be used to assess the robustness of the primary analysis approach, in the event the primary analysis is positive. Missing data are first imputed for all visits under the missing-at-random (MAR) assumption, and then a worsening/shift is applied. This is repeated until the result is no longer statistically significant (i.e., p>0.05). The tipping point (smallest worsening/shift in which the significant result turns non-significant) provides a measure of robustness of the primary result. Additionally, in the event the primary analysis is positive a multiple

Form STAT401.V3 Page 13 of 23

Client/Project	Arrivo/Sirtsei 201
Version and Date	V01 August 26, 2022

imputation analysis will be performed with 100 imputations of the study data using available results and variables used in the primary analysis (week, treatment, week to treatment interaction, and baseline MADRS score) to model missing data for each treatment group. Each imputed dataset will be analyzed separately using the same MMRM model in the primary efficacy analysis. The estimates from the imputed model analyses will be combined for statistical inference.

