# 10 List of Tables, Figures and Listings

# 10.1 List of Tables

Table Number	Title	Population	Included in Top Line Results Package
14.1.1	Subject Accountability	All Subjects	Yes
14.1.2.1	Subject Disposition	All Subjects	Yes
14.1.2.2	Protocol Deviations	Safety	
14.1.3	Demographics	Safety	Yes
14.1.4	Body Measurements at Screen and Baseline	Safety	
14.1.5	Medical History	Safety	
14.1.6.1	Concomitant Medications during the Treatment Period	Safety	
14.1.6.2	Concomitant Medications during the Follow-up Period	Safety	
14.1.7.1	Depression and Current Depressive Episode History	mITT	
14.1.7.2	Current Depressive Episode – Current Treatment at Screen	mITT	
14.1.7.3	Current Depressive Episode – Previous Treatments	mITT	
14.1.8	Treatment Administration and Compliance	Safety	Yes
14.2.1.1	Primary Efficacy Analysis Change from Baseline MADRS Score at Week 4 Using Mixed Models for Repeated Measures	mITT	Yes
14.2.1.2	Analysis of the Change from Baseline Total MADRS Score at Week 4 Type 3 Model Effects	mITT	
14.2.2.1	Tipping Point Analysis of Primary Efficacy Endpoint	mITT	
14.2.2.2	Multiple Imputation Analysis of Primary Efficacy Endpoint	mITT	
14.2.2.3	Covariate Analysis Effect of Age on Primary Efficacy Endpoint	mITT	
14.2.2.4	Test for Homogeneity of Site on Primary Efficacy Endpoint	mITT	
14.2.3.1	Change from Baseline to pre- Week 4 Timepoints in MADRS Score Using MMRM	mITT	Yes
14.2.3.2	Analysis of the Change from Baseline Total MADRS Score pre-Week 4 Timepoints Type 3 Model Effects	mITT	
14.2.4.1	Change from Baseline to Week 5 in MADRS Score and Change	mITT	Yes

Form STAT401.V3 Page 18 of 23

Client/Project	Arrivo/Sirtsei 201
Version and Date	V01 August 26, 2022

Table Number	Title	Population	Included in Top Line Results Package
	from Week 4 to Week 5 in MADRS Score		
14.2.4.2	Analysis of the Change from Baseline to Week 5 and Week 4 to Week 5 Total MADRS Score Type 3 Model Effects	mITT	
14.2.5.1	Change from Baseline CGI-S Score Over Time	mITT	Yes
14.2.5.2	Analysis of the Change from Baseline CGI-S Score Over Time Type 3 Model Effects	mITT	
14.2.6.1	Change from Baseline to Week 5 in CGI-S Score and Change from Week 4 to Week 5 in CGI-S Score	mITT	Yes
14.2.6.2	Analysis of the Change from Baseline to Week 5 and Week 4 to Week 5 CGI-S Type 3 Model Effects	mITT	
14.2.7.1	Change in HAM-D-17 Score Over Time	mITT	Yes
14.2.7.2	Analysis of the Change from Baseline HAM-D-17 Score Over Time Type 3 Model Effects	mITT	
14.2.8.1	Change in SDS Score Over Time	mITT	

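### The tipping-point analysis runs on mITT, so dosed subjects who leave before any post-dose rating escape the shift and the result can look more robust than it is

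*SAP*

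**What the plan says.** SAP section 7 defines mITT as subjects who were randomised, took at least one dose, "and have a Baseline and at least one post-dose" efficacy assessment. Section 8.1 adds that treated subjects with no post-treatment "follow-up assessments or data will be listed, but not analyzed". Section 8.3.5.1 fixes the set for efficacy: "Efficacy analyses will be conducted using the mITT population, assuming subjects had dosed as directed for 4 weeks".

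Section 8.3.5.2 describes the hypothetical approach to leaving early: the "strategy was selected for premature discontinuation or treatment discontinuation intercurrent events to evaluate the effect of treatment" in terms of pharmacologic efficacy. Table 8.1 assumes that a leaver follows the course of subjects in the same arm who stayed on treatment. It makes no exception for those who leave before the first rating.

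Section 8.3.5.5 says that, if the primary analysis is positive, "a sensitivity analysis using the tipping-point approach may be used to assess the robustness of the" primary approach. The method is: "Missing data are first imputed for all visits under the missing-at-random (MAR) assumption, and then a worsening/shift is applied". The shift grows until significance is lost. The arm to be shifted is not named, and no tipping-point value is set as adequate. In section 10.1, "Tipping Point Analysis of Primary Efficacy Endpoint" (Table 14.2.2.1) and "Multiple Imputation Analysis of Primary Efficacy Endpoint" (Table 14.2.2.2) both carry the population label mITT. No sensitivity analysis uses all randomised or all dosed subjects.

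**The concern.** A tipping-point analysis asks how much worse than expected the unseen outcomes would have to be before the result fails. Subjects who take a dose and leave with no rating are those for whom missing-at-random has least support, because nothing after Baseline is known about them. The method could include them, imputing from arm and Baseline score, but the mITT label removes them first. The shift then falls on a smaller share of the SP-624 arm, so a larger shift is needed to lose significance.

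This matters more here than it might elsewhere. The tipping point is the only sensitivity analysis in the SAP that departs from missing-at-random; the pattern-mixture analysis in protocol section 9.3.5 is not carried into it. The dropout plots do not fill the gap, since their categories begin with Week 1 dropouts. The exclusion also happens after randomisation and may differ by arm. The sponsor has already dropped the mITT condition from the safety population and described that as a correction (SAP section 2.2). The same step was not taken for the robustness check.

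**Working it through.** **Inputs from the documents.** 150 per arm, difference 3 units, SD 9.2, 80% power (SAP section 5); two-sided 0.05 (protocol section 9.3.1); dropout 20-30%, given as typical of MDD studies with no denominator stated (SAP section 8.3.5.5).

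**Inputs not in the documents.** The share e of dosed subjects with no post-dose rating, and the arm shifted. I take e = 2%, 5% and 8%, and a shift in the SP-624 arm only. Both are assumptions.

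**The plan's own figure.** 2 × (1.960 + 0.842)² × 9.2² / 3² gives 148 per arm; the t-test version gives 149, with 80.4% power at 150. The stated 150 reproduces. The documents give no tipping point to reproduce.

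**Formula.** Let G be the missing-at-random treatment difference minus the critical value times its standard error. Adding a shift to every imputed Week 4 score in the SP-624 arm moves that arm's mean by shift × f, where f is the imputed share. Significance is lost at about shift = G / f.

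- All dosed subjects: f = d.
- mITT: f = (d - e) / (1 - e).
- Unrated subjects add almost nothing to the missing-at-random estimate or its standard error, so G is nearly the same in both sets.
- Ratio of tipping points, mITT to all dosed: d(1 - e) / (d - e).

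Example, d = 25% and e = 5%: 0.25 × 0.95 / 0.20 = 1.19, or 19% too large.

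| d | e = 2% | e = 5% | e = 8% |
|---|---|---|---|
| 20% | +9% | +27% | +53% |
| 25% | +6.5% | +19% | +35% |
| 30% | +5% | +14% | +25% |

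**Simulation check.** With 150 per arm, a true difference of 4 units, by-arm regression imputation, 100 imputations, Rubin's rules and 40 significant trials per setting, the median overstatements were +10/+29/+50% (d = 20%), +7/+20/+33% (d = 25%) and +6/+16/+24% (d = 30%). They agree with the formula.

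**In MADRS units.** Assume an observed difference of 4 units, d = 25% and e = 5%. There are 150 × 0.75 = 112.5 observed per arm; SE = 9.2 × √(2/112.5) = 1.227; G = 4 - 1.96 × 1.227 = 1.60. The tipping shift is 1.60 / 0.25 = 6.4 on all dosed subjects, and 1.60 / 0.2105 = 7.6 on mITT.

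**Two variations.**

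- Constant weekly dropout, with everyone who leaves in the first of the four weeks unrated (assumptions): e = 1 - (1 - d)^(1/4) = 5.4% at d = 20% and 8.5% at d = 30%. The ratios are 1.30 and 1.28, so +28% to +30%.
- If 20-30% is instead the missing share m within mITT, the ratio is (e + (1 - e)m) / m. For e = 2-8% this gives +5% to +32%.

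**The case against.** The strongest reply is that few subjects may be lost in this way.

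- Protocol section 5.4 asks sites to attempt the Week 4 / Premature Discontinuation procedures for everyone who stops, and those include MADRS and CGI-S.
- Any post-dose efficacy assessment gives entry to mITT, not only a MADRS.
- SAP section 8.1.1 removes visits made 3 or more days after the last dose from the treatment-period analysis. A subject whose only rating is such a visit can still be in mITT with all four visits missing, and would then be imputed and shifted. Some of the earliest leavers are therefore already in the stress test.
- If half of the leavers assumed under constant weekly dropout were rated, the overstatement would be about 12% at each dropout rate.

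This stands as a reason to treat e as unknown. It is not a reason to take e as zero: protocol section 7.2.4 bars rating a subject who has missed two or more consecutive doses just before a treatment visit, and the discontinuation visit cannot be remote. These push e upward.

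It is also fair that the analysis is optional, follows only a positive primary result, and has no threshold attached, so no declared decision turns on it. But a positive result is exactly when its robustness would be cited.

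A reader might infer more than the documents support:

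- **That the overstatement is a quarter to a third.** That needs about 24-32% of all dropouts to leave unrated, a share the documents do not give.
- **That the multiple-imputation result is biased too.** It applies no shift, and under missing-at-random a subject known only by arm and Baseline adds almost no information.
- **That the 3-unit effect would shrink by a stated amount if early leavers had no change.** That is a different assumption about their outcome, at odds with the hypothetical strategy in Table 8.1, and is not a tipping-point result.

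**Conclusion.** The point holds for the tipping-point analysis. On mITT, dosed subjects with a Baseline MADRS and no post-dose rating escape the shift. With the shift in the SP-624 arm only, this makes the tipping point too large by about 5% to 53% for e = 2-8% and d = 20-30%. The direction is firm under that one-arm shift; the size depends on e, which only the trial data can supply. If both arms are shifted equally, the answer depends on the difference in missingness between arms and this ratio does not apply. The primary MMRM is unaffected, because a subject with no post-baseline score adds nothing to its likelihood. I rate this a cheap improvement.

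**What to change.** - In SAP section 8.3.5.5, run the tipping-point analysis on all randomised subjects who took at least one dose and have a Baseline MADRS, by randomised arm. Impute Weeks 1-4 for those with no post-dose score and include them in the shift.
- State which arm is shifted.
- Report the number per arm with no post-dose MADRS.
- Change the population label of Table 14.2.2.1.
- Add a matching exception to the section 8.1 sentence on treated subjects without later data, and to the mITT statement in section 8.3.5.1. Without these the new text would contradict both.

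Keep the primary MMRM on mITT. Changing Table 14.2.2.2 is optional.

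The cost is a few sentences and one table label, with no new data collected. The reported tipping point will be less favourable, and the added subjects are imputed from arm and Baseline score alone.
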